#### Table 1:Schedule of Events

						_					End of Treatment/Early Termination/
	Treatment Period								End of Study 		
Study Procedure	Visit 1	Visit 2	Visit 3	Visit 4	Visit 5	Visit 6	Visit 7	Visit 8	Visit 9	Visit 10	Visit 11
Day	1										
Week	0	8	12	24	48	72	96	120	144	168	192
Visit Window (days)		±3	±3	±3	±3	±3	±3	±3	±3	±3	±3
Screening/Baseline:											
Inclusion/Exclusion	X										
Informed Consent	Х										
Demographics	Х										
Prior Medication History	Х										
IVRS/IWRS	Х	X	Х	Х	Х	Х	Х	Х	Х	Х	
Treatment:											
Review of Diet	X	X	X	Х	X	X	X	Х	Х	X	X
Administer Study Drug	X 										
Study Drug Kit Dispensation 	Х	Х	X	Х	X	X	Х	Х	Х	X	
Concomitant Medication 	Х	Х	Х	Х	X	Х	Х	Х	Х	X	Х
Patient Drug Log Dispensation/Collection	Х	X	X	Х	Х	Х	Х	Х	Х	X	Х
Safety:											
Vital Signs	Х				X		X		X		X
Physical Examination and Body Weight	Х				Х		Х		Х		Х
Adverse Events	Х	Х	Х	Х	Х	Х	Х	Х	Х	Х	Х
Efficacy:											
Total-C, LDL-C, HDL- C, TG, non-HDL-C 	X 	X		X	X	X	X	Х	Х	X	X
Apo B, Apo A-1, Lp(a)	X 				Х		Х		Х		Х
Laboratory Testing:											
Hematology	X 			Х	X	Х	Х	Х	Х	X	X

**Regeneron Pharmaceuticals, Inc.** 

CONFIDENTIAL

Page 30 of 57

	Treatment Period							End of Treatment/Early Termination/ End of Study 			
Study Procedure	Visit 1	Visit 2	Visit 3	Visit 4	Visit 5	Visit 6	Visit 7	Visit 8	Visit 9	Visit 10	Visit 11
Day	1										
Week	0	8	12	24	48	72	96	120	144	168	192
Visit Window (days)		±3	±3	±3	±3	±3	±3	±3	±3	±3	±3
Blood Chemistry	$X^7$			Х	Х	Х	Х	Х	Х	Х	Х
Urinalysis	$X^7$			Х	Х	Х	Х	Х	Х	Х	Х
hs-CRP	$X^7$			Х	Х	Х	Х	Х	Х	Х	Х
Gonadal Hormones & Gonadotropins 	$\mathbf{X}^7$			Х	Х	Х	Х	Х	Х	Х	Х
Urine Pregnancy Test (for women of childbearing potential)	X 	X	X	Х	Х	Х	Х	Х	Х	Х	Х
Research Testing											
Research Samples (serum/plasma)	$X^7$				Х		Х		Х		Х

#### 8.1.1. Footnotes for the Schedule of Events Table

- 1. Patients who prematurely discontinue study treatment: any study treatment discontinuation should be initially considered temporary, and the investigator should make every effort to resume study drug treatment as early as possible, pending no safety concerns, and to perform all study visits and assessments as usual. When a treatment discontinuation is considered 'permanent', an extra visit (early termination visit) should be performed within 5 days of the decision to permanently discontinue study drug. This visit will be the last visit for the patient.
- 2. The end of study (EOS) visit of the double-blind neurocognitive function study (R727-CL-1532) corresponds to visit 1 (day 1) of the OLE study. Patients may enroll in the OLE study after completing treatment and the EOS visit in the neurocognitive function study (R727-CL-1532). The first SC injection of PRALUENT will be administered in the clinic (day 1, visit 1). After visit 1, patients have the option to either self-administer study drug, or have another designated person (such as a spouse or caregiver) administer study drug for them. Study drug should be administered Q2 weeks throughout the study.
- 3. The kit will include study drug and the study drug compliance log.
- 4. If at any time during the study after the week 8 visit, the investigator, based on lipid results or safety issue, decides to modify the dose of study drug, an unscheduled kit dispensation visit will be performed. During this visit, a call to the IVRS/IWRS will be performed.
- 5. Concomitant medication: received concomitantly to the study drug, from the time of informed consent to the final study visit.
- 6. Alcohol consumption within 48 hours and intense physical exercise within 24 hours prior to blood sampling for lipid parameters are discouraged.
- 7. Assessments completed at EOS in the neurocognitive function study (R727-CL-1532).
- 8. For male patients (luteinizing hormone [LH], follicle-stimulating hormone [FSH], and testosterone) and for female patients (LH, FSH, and estradiol). Menstrual cycle data will be collected for women of childbearing potential who are not on hormonal contraceptives.

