# 4.2. Primary and Secondary Endpoints

## 4.2.1. Primary Endpoint

The primary endpoint in the study is the incidence of AEs after first administration of study drug through the last dose of study drug plus 2 weeks.

The following AEs will be described:

- AEs/serious adverse events (SAEs)
- AEs leading to treatment discontinuation
- Adverse events of special interest (AESI)

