### 9.4.6. Follow-up

Adverse event information will be collected until the patient's last study visit.

Serious adverse event and AESI information will be collected until the event is considered chronic and/or stable.

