### 10.4.4.1. Adverse Events

### **Definitions**

For safety variables, the following observation periods are defined:

- The pretreatment period is defined as the time from signing the ICF to before the first dose of study drug.
- The TEAE period is defined as the day from first dose of study drug to the last study visit.

Pretreatment AEs are defined as those that developed, worsened, or became serious during the pretreatment period

Treatment-emergent adverse events (TEAEs) are defined as those that are not present at baseline or represent the exacerbation of a pre-existing condition during the on-treatment period.

Post-treatment AEs are defined as those that developed, worsened, or became serious during the post-treatment period.

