4.7.1. Adverse Events Variables

The period of safety observation starts from the time when the patient gives informed consent and continues into the following periods:

- The PRE-TREATMENT period: defined as the time from the signed informed consent up to the first study treatment injection.
- The treatment-emergent adverse event (TEAE) period: defined as the time from the first dose of study drug to the last study visit.
- The POST-TREATMENT period: defined as starting the day after the end of the TEAE periods up to the patient's end of study.

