5.7.1. Analysis of Adverse Events

In general, the primary focus of AE reporting will be on TEAEs. Pre-treatment and post-treatment AEs will be provided separately.

If an AE date/time of onset (occurrence, worsening, or becoming serious) is incomplete, an imputation algorithm will be used to classify the AE as pre-treatment, treatment-emergent, or post-treatment. The algorithm for imputing date/time of onset will be conservative and will classify an AE as treatment-emergent unless there is definitive information to determine pre-treatment or post-treatment status. Details on classification of AEs with missing or partial onset dates are provided in Section 6.4.

Adverse event incidence tables will present the number (n) and percentage (%) of patients experiencing an AE by SOC, HLGT (when applicable), HLT (when applicable), and PT. Multiple occurrences of the same event in the same patient will be counted only once in the tables within a treatment phase. For tables presenting severity of events, the worst severity will be chosen for patients with multiple instances of the same event. The denominator for computation of percentages is the safety population within each patient group.

The table of all TEAEs presented by SOC and PT will be sorted by the internationally agreed SOC order and decreasing frequency of PTs within SOCs (in the PRALUENT group). This will define the presentation order for all other tables by SOC and PT, unless otherwise specified. The tables of AEs by SOC, HLGT, HLT and PT will be sorted by the SOC internationally agreed order and the other levels (HLGT, HLT, PT) will be presented in alphabetical order, unless otherwise specified.

Analysis of all treatment-emergent adverse events

The following TEAE summaries will be generated:

- Overview of TEAEs, summarizing number (%) of patients with any
 - TEAE;
 - Serious TEAE;
 - TEAE leading to death;
 - TEAE leading to permanent treatment discontinuation.
- All TEAEs by primary SOC, HLGT, HLT, and PT
- Number (%) of patients experiencing common TEAE(s) presented by primary SOC, HLT and PT (HLT incidence ≥ 5 % in the total patient group), sorted by SOC internationally agreed order and by alphabetic order for the other levels (HLT and PT);
- All TEAEs by primary SOC and PT, sorted by the internationally agreed SOC order and by decreasing incidence of PTs within each SOC (in the PRALUENT group).

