- All TEAEs regardless of relationship in one column and, in the same table a second column with TEAEs related to alirocumab according to investigator's opinion by primary SOC, HLGT, HLT and PT;
- All TEAEs by maximal severity (i.e., mild, moderate or severe), presented by primary SOC and PT, sorted as defined above;
- The event rate per patient-year (the number of patients with an event in question divided by total patient-years) will be provided for all TEAEs by SOC and PT. For a patient with event, patient year is censored at time of first event; for patient without event, it corresponds to length of TEAE period;
- Kaplan-Meier curves will be provided, when appropriate, for time from first dose of study treatment to the first occurrence of selected TEAEs as well as incidence

rates at 48, 96, 144, and 192 weeks of exposure. Patients without any event will be censored at the end of the TEAE period. Selected TEAEs could be AESIs (e.g neurocognitive events), or TEAE related to any clinically significant signal that needs further characterization;

The frequency of selected AEs by SOC and PT over time during the treatment period (number of patients experiencing AE and percentage by patient-months) will be provided, when appropriate, by time intervals defined as: ≤48 weeks, >48 to ≤96 weeks, >96 to ≤144 weeks, >144 to ≤192 weeks, using the PROC LIFETEST with the actuarial method. Only the first event will be counted.

Analysis of all treatment emergent serious adverse event(s)

- All serious TEAEs by primary SOC, HLGT, HLT, and PT and by SOC/PT; Patient listings of serious TEAEs will be provided for the report appendix.
- All serious TEAEs regardless of relationship in one column and in the same table a second column with TEAEs related to alirocumab according to investigator's opinion, by primary SOC, HLGT, HLT, and PT;
- The event rate per patient-year will be provided for all serious TEAEs by SOC and PT.

Analysis of all treatment-emergent adverse event(s) leading to treatment discontinuation

• All TEAEs leading to permanent treatment discontinuation, by primary SOC, HLGT, HLT, and PT and by SOC/PT; Patient listings of TEAEs leading to permanent treatment discontinuation will be provided for the report appendix.

Analysis of groupings of adverse events including selected adverse events of special interest

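### The primary adverse-event window (to last dose plus 14 days) and the TEAE period (to last visit) do not coincide; the mismatch runs both ways and is numerically small

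*Protocol*

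**What the plan says.** - **Primary window.** Protocol 4.2.1 and SAP 4.6.1 define the primary endpoint as the incidence of AEs from first administration "through the last dose of study drug plus 2 weeks".
- **Last visit after a permanent stop.** Footnote 1 in Protocol 8.1.1 says that "any study treatment discontinuation should be initially considered temporary". Once a stop is judged permanent, the early termination visit is due "within 5 days of the decision to permanently discontinue study drug. This visit will be the last visit for the patient". Protocol 8.1.2 asks for this visit as soon as practicable and at most 1 month after the last injection. Neither place sets a minimum interval after the last dose.
- **End of AE collection.** Protocol 9.4.6: "Adverse event information will be collected until the" patient's last study visit.
- **TEAE period.** Protocol 10.4.4.1: "The TEAE period is defined as the day from first dose of study drug to the last study visit". SAP 4.7.1 has the same period, "defined as the time from the first dose of study drug to the last study visit", and classes anything later as post-treatment.
- **Serious events.** Protocol 9.4.2 has SAEs reported if onset is within 30 days after the end-of-study or early termination visit.
- **Tables.** SAP 5.7.1 puts the main focus on TEAEs and describes no separate table for the primary window. "Multiple occurrences of the same event in the same patient will be counted only once in the tables within a treatment phase". For patient-year rates, "for patient without event, it corresponds to length of TEAE period".

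**The concern.** The endpoint and the period used to tabulate it are anchored to different dates, last dose plus 14 days and last visit. They agree only when the last visit falls exactly 14 days after the last dose.

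If the visit is earlier, part of the primary window is unobserved for ordinary non-serious AEs. New non-serious AESIs may be affected too, because Protocol 9.4.3 does not say what happens when onset follows the last visit. An SAE in those days is reported to the sponsor but leaves the treatment-emergent tables, although the primary definition includes it. If the visit is later, the TEAE tables include events that the primary definition excludes.

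At stake is whether the reported primary result is the quantity defined. No test, comparison or decision threshold depends on it.

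**Working it through.** The plan gives no figure for this point, so there is none to reproduce.

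**Step 1. Days of the primary window not observed (documents only).** Let d be the days from last dose to the permanent decision, and lag the days from decision to visit (0 to 5, footnote 1).

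Lost days = max(0, 14 − d − lag)

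| Decision day d | Lost days (lag 5 to lag 0) |
|---|---|
| 0 | 9 to 14 |
| 4 | 5 to 10 |
| 8 | 1 to 6 |
| 9 | 0 to 5 |
| 14 or later | 0 |

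For d from 0 to 8 a loss is certain under footnote 1. From 9 to 13 it depends on the lag.

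**Step 2. Days counted beyond the window (documents only).** Protocol 8.1.2 allows the visit up to 1 month after the last injection. Taking a month as 30 days, the TEAE period can exceed the window by 30 − 14 = 16 days. For completers, with the last dose at about week 190 and the week 192 visit at ±3 days, the visit falls 11 to 17 days after the last dose: up to 3 days short or 3 days over.

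**Step 3. Size of the missed part (assumed inputs).** The documents do not give the share stopping early (s), the first-event rate for one AE type (r per year), the time of stopping (T years), or the share of decisions at day 14 or later (f). Because a patient counts once per event, only those with no earlier event of that type can add to a crude percentage:

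Missed = s × (1 − f) × exp(−rT) × E[1 − exp(−r × lost/365.25)]

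With d spread evenly over 0 to 14 and lag over 0 to 5:
- Mean lost days = (14³ − 9³)/(3 × 5 × 28) = 2015/420 = 4.80.
- Share with any loss = (14 − 2.5)/14 = 82%.

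For s = 0.20, r = 0.5, T = 1, f = 0: 0.20 × 0.607 × (0.5 × 4.80/365.25 = 0.0066) ≈ 0.0008, or 0.08 points. This is about 1.3 of 1600 planned patients, against a crude incidence of 1 − exp(−0.5) = 39.3%.

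| s | r | f | T = 1 year | T = 2 years |
|---|---|---|---|---|
| 0.20 | 0.5 | 0 | 0.079 | 0.048 |
| 0.20 | 0.5 | 0.5 | 0.040 | 0.024 |
| 0.20 | 0.5 | 0.9 | 0.008 | 0.005 |
| 0.20 | 0.05 | 0 | 0.012 | 0.012 |
| 0.20 | 1 | 0 | 0.096 | 0.035 |
| 1.00 | 0.5 | 0 | 0.396 | 0.240 |

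(Percentage points.) With s = 0.20 the maximum over r is 0.096 at one year and 0.048 at two. Earlier stopping gives more: 0.10 at six months with r = 0.5. If half of the stoppers are still event-free at 2 events per year, 20% stopping with a 5.1-day gap gives 0.28 points, and 30% all losing 14 days gives 1.1.

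**Step 4. Size of the opposite part (same assumptions).** If the 20% who stop all had their visit at day 30, events counted beyond the window at r = 0.5 and T = 1 would be 0.20 × exp(−0.5 × (1 + 14/365.25)) × (1 − exp(−0.5 × 16/365.25)) = 0.26 points. That is also an extreme case, but it shows that the excess can outweigh the loss.

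**The case against.** **Stops are first treated as temporary.** Protocol 7.3.2.2 defines an interruption as at least one scheduled injection not given. With dosing every 2 weeks, the first missed injection is due at about day 14, and a decision then loses nothing. This stands: an even spread over days 0 to 14 is an unfavourable assumption, and the rows with f = 0.5 or 0.9 may be nearer the truth. It does not remove prompt permanent stops. Protocol 7.3.2.1 lists pregnancy, acute injection reaction of clinical concern, and patient request.

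**Other provisions may cover the gap.** Protocol 9.4.1 records AEs until end of study, 8.1.3 permits unscheduled visits, and SAP 5.7.1 tabulates post-treatment AEs and SAEs. These help only in part. No contact is scheduled after the last visit, 9.4.6 is specific to the individual patient's visit, and an SAE shown as post-treatment is visible but outside the primary count.

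**Ending at the last visit was deliberate.** Amendment 2 dropped follow-up after discontinuation because the objective rests on actual exposure. However, the exposure formula in Protocol 10.4.4.3 itself credits 14 days after the last dose, so following AEs to day 14 fits that reasoning.

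**Stronger readings.** A reader might infer that the primary incidence is biased downward. The documents do not support a net direction, because late visits add events outside the window. A reader might also infer that serious events or AEs leading to discontinuation are lost. They are not: the 30-day rule covers the former, and the latter begin before the decision and hence before the visit. Nor are patient-year rates and Kaplan-Meier estimates distorted by unobserved days, since both end follow-up with the TEAE period.

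**Conclusion.** The inconsistency is real and present in the current text of both documents. In patients whose permanent decision comes 0 to 8 days after the last dose, the primary endpoint cannot be fully observed as defined. In patients seen after day 14, the TEAE tables exceed it. These statements need only date arithmetic.

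The size rests on assumptions. With 20% stopping early, at one year or later, the missed part stays below 0.1 points for any single event type. It is larger if patients stop early at high event rates. The 0.40-point figure at one year for all patients applies only if everyone was closed out this way after the sponsor's termination, and the documents do not describe that procedure. The excess part is of similar or larger order, so the net sign is unknown.

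SAP 1.1 makes all analyses descriptive. This is a minor point about making the reported endpoint match its definition, and it does not threaten the study's conclusions.

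**What to change.** **SAP, still feasible:**

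1. For the crude primary-endpoint tables, count recorded AEs with onset, worsening or becoming serious from first dose through last dose plus 14 days, including SAEs reported after the last visit.
2. Keep patient-years and Kaplan-Meier censoring at the last visit, where AE collection ends. Simply extending the TEAE period to day 14 would add days without AE collection to the time at risk and bring a small downward bias into estimates that now avoid it.
3. Report the number of patients whose last visit came before last dose plus 14 days.

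The cost is one definition and one extra count. SAP 6.3 already has a rule for a missing last injection date.

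**Protocol, only if the text is reused:** in 9.4.1 and 9.4.6, collect AEs to the later of the last visit and last dose plus 14 days, with a brief phone contact when the visit is earlier. This is a minor site workload.

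The sponsor terminated the study on January 31, 2020, so only the SAP part can still be done, and it cannot recover non-serious AEs that were never collected.

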#### 8.1.2. Early Termination Visit

This visit is only to be done for patients who discontinue the treatment prematurely, whatever the reason, and will take place as soon as practically possible (within 1 month after the last injection of PRALUENT). For patients who prematurely permanently discontinue study drug, see Section 7.3.2.

#### 8.1.3. Unscheduled Visits

All attempts should be made to keep patients on the study schedule. Unscheduled visits may be necessary to repeat testing following abnormal laboratory results, for follow-up of AEs, or for any other reason, as warranted.

## 8.2. Study Procedures

#### 8.2.1. Procedures Performed Only at the Screening/Baseline Visit

The following procedures will be performed for the sole purpose of determining study eligibility: inclusion/exclusion criteria.

**Regeneron Pharmaceuticals, Inc.** 

CONFIDENTIAL

Page 32 of 57

## 8.2.2. Safety Procedures

## 8.2.2.1. Vital Signs

Vital signs, including temperature, sitting blood pressure, and pulse will be collected at time points indicated in Table 1.

## 8.2.2.2. Physical Examination and Body Weight

A general physical examination including body weight will be performed at time points indicated in Table 1.

If a new clinically significant abnormality or worsening from baseline is detected after informed consent, the patient should be considered for further clinical investigation and/or specialist consultation at the investigator's discretion.

Body weight will be obtained with the patient wearing undergarments or very light clothing and no shoes, and with an empty bladder. The same scale should be used throughout the study.

Calibrated balance scales should be used to guarantee accuracy of patients' weight. Self-reported weights are not acceptable, and patients must not read the scales themselves.

## 8.2.2.3. Laboratory Testing

Hematology, chemistry, urinalysis, and pregnancy testing samples will be analyzed by a central laboratory. A liver panel will be forwarded to the central laboratory. In case of total bilirubin values above the normal range, differentiation into conjugated and nonconjugated bilirubin will occur automatically.

Detailed instructions for blood sample collection are in the laboratory manual provided to study sites.

Samples for laboratory testing will be collected at visits at time points according to Table 1. Tests will include:

#### Blood Chemistry

Sodium	Total protein, serum	Total bilirubin
Potassium	Creatinine	Uric acid
Chloride	Blood urea nitrogen (BUN)	Creatine phosphokinase (CPK)
Carbon dioxide	AST	γGT
Calcium	ALT	HbA1c
Glucose	Alkaline phosphatase	
Albumin	Lactate dehydrogenase (LDH)	

#### Hematology

Hemoglobin	Differential:
Hematocrit	Neutrophils
Red blood cells (RBCs)	Lymphocytes
White blood cells (WBCs)	Monocytes
Red cell indices	Basophils
Platelet count	Eosinophils

#### Urinalysis

Color	Glucose	RBC
Clarity	Blood	Hyaline and other casts
pН	Bilirubin	Bacteria
Specific gravity	Leukocyte esterase	Epithelial cells
Ketones	Nitrite	Crystals
Protein	WBC	Yeast

#### **Other Laboratory Tests**

Pregnancy testing (urine) will be performed for women of childbearing potential at time points according to Table 1.

Samples for high-sensitivity C-reactive protein (hs-CRP), and gonadal hormones (for female patients - estradiol, follicle-stimulating hormone [FSH] and luteinizing hormone [LH]; for male patients – testosterone, FSH and LH) will be collected at time points according to Table 1.

#### Abnormal Laboratory Values and Laboratory Adverse Events

- All laboratory values must be reviewed by the investigator or authorized designee.
- Significantly abnormal test results that occur after start of treatment must be repeated to confirm the nature and degree of the abnormality. When necessary, appropriate ancillary investigations should be initiated. If the abnormality fails to resolve or cannot be explained by events or conditions unrelated to the study medication or its administration, the medical monitor must be consulted.

• The clinical significance of an abnormal test value, within the context of the disease under study, must be determined by the investigator.

Criteria for reporting laboratory values as an AE are provided in Section 9.4.5.

